3.0 BACKGROUND DRUG INFORMATION

3.1 Lenalidomide

Celgene Corporation will supply Revlimid® (lenalidomide) to study participants at no charge through the RevAssist® program. All physicians who prescribe lenalidomide for research subjects enrolled into this trial and all research subjects enrolled into this trial must be registered in and must comply with all requirements of Celgene's RevAssist® program.

Dosage form

Lenalidomide will be supplied as 5 mg capsules for oral administration.

Packaging

Lenalidomide will be shipped directly to the patient through the Celgene's RevAssist® program.

Prescribing Information

Lenalidomide (Revlimid®) will be provided to research subjects for the duration of their participation in this trial at no charge to them or their insurance providers. Lenalidomide will be provided in accordance with the RevAssist® program. Per standard RevAssist® requirements all physicians who prescribe lenalidomide for research subjects enrolled into this trial, and all research subjects enrolled into this trial, must be registered in and must comply with all requirements of Celgene's RevAssist® program. Prescriptions must be filled within 7 days. Only enough lenalidomide for one cycle of therapy will be supplied to the patient each cycle.

3.2 Prednisone

Prednisone will be used from commercially available supplies.

4.0 PATIENT ELIGIBILITY CRITERIA

4.1 Inclusion criteria

1. Diagnosis of myelofibrosis requiring therapy, including those previously treated and relapsed or refractory, or if newly diagnosed, with intermediate or high risk according to Lille scoring system (risk factors are: Hb < 10 g/dl, WBC < 4 or > 30 x 10⁹/L; risk group: 0 factor(s) = low, 1 factor(s) = intermediate, 2 factor(s) = high) or with symptomatic splenomegaly.
2. Understanding and voluntary signing an IRB-approved informed consent form.
3. Age ≥ 18 years at the time of signing the informed consent.
4. Disease-free of prior malignancies for ≥ 2-years with exception of basal cell or squamous cell carcinoma of the skin, or carcinoma "in situ" of the cervix or breast.
5. ECOG performance status 0 to 2.
6. Patients must have adequate organ function as demonstrated by the following:
 - Total bilirubin ≤ 2.0 mg/dL (unless higher due to MF).
 - Serum creatinine ≤ 2.0 mg/dL (unless higher due to MF).
 - Absolute neutrophil count ≥ 1 x 10⁹/L
 - ALT ≤ 3 x upper limit of normal (unless higher due to MF)

7. Females of childbearing potential (FCBP)[†] must have a negative serum or urine pregnancy test with a sensitivity of at least 50 mIU/mL within 10 – 14 days prior to and again within 24 hours of starting lenalidomide and must either commit to continued abstinence from heterosexual intercourse or begin TWO acceptable methods of birth control, one highly effective method and one additional effective method AT THE SAME TIME, at least 4 weeks before she starts taking lenalidomide. FCBP must also agree to ongoing pregnancy testing. Men must agree to use a condom during sexual contact with a female of child bearing potential even if they have had a successful vasectomy. All patients must be counseled at a minimum of every 28 days about pregnancy precautions and risks of fetal exposure. See Appendix J: Risks of Fetal Exposure, Pregnancy Testing Guidelines and Acceptable Birth Control Methods.
8. All study participants must be registered into the mandatory RevAssist@ program, and be willing and able to comply with the requirements of RevAssist@.

4.2 Exclusion Criteria

1. Use of any other standard (e.g. hydroxyurea, anagrelide, growth factors) or experimental drug or therapy within 28 days of starting lenalidomide and/or lack of recovery from all toxicity from previous therapy to grade 1 or better.
2. Known prior clinically relevant hypersensitivity reaction to thalidomide, including the development of erythema nodosum if characterized by a desquamating rash.
3. Prior therapy with lenalidomide.
4. Any serious medical condition, laboratory abnormality, or psychiatric illness that would prevent the subject from signing the informed consent form.
5. Suspected Pregnancy, Pregnant or lactating females.
6. Any condition, including the presence of laboratory abnormalities, which places the subject at unacceptable risk if he/she were to participate in the study or confounds the ability to interpret data from the study.
7. Known positive for HIV or infectious hepatitis, type A, B or C.
8. Known prior clinically relevant hypersensitivity to prednisone.
9. Participants with heart rate (HR) of less than or equal to 50, as a HR less than 50 indicates underlying cardiac abnormalities.

[†] A female of childbearing potential is a sexually mature woman who: 1) has not undergone a hysterectomy or bilateral oophorectomy; or 2) has not been naturally postmenopausal for at least 24 consecutive months (i.e., has had menses at any time in the preceding 24 consecutive months).

10. Participants with prior history of thromboembolic disease (i.e. deep venous thrombosis (DVT) or pulmonary embolism (PE) within the last six months, as Lenalidomide has demonstrated a significantly increased risk of DVT or PE.
11. Participant is unwilling or unable to comply with the RevAssist® Program.

5.0 TREATMENT PLAN

The planned dose and schedule of investigation of lenalidomide is 10 mg/day orally (unless blood platelet count is below $100 \times 10^9/L$, in which case the starting dose of lenalidomide is 5 mg/day). Lenalidomide will be taken orally in the morning each day on days 1-21, followed by 7 days of no therapy of each 28-day cycle.

Lenalidomide capsules should be swallowed whole, and should not be broken, chewed or opened. If a dose of lenalidomide is missed, it should be taken as soon as possible on the same day. If it is missed for the entire day, it should not be made up.

Patients who take more than the prescribed dose of lenalidomide should be instructed to seek emergency medical care if needed and contact study staff immediately. Twenty eight days is considered one cycle of therapy. Attempts will be made to provide an adequate treatment period of at least 6 months unless significant toxicity observed, to account for delayed time to response observed with biologic agents. Responders will continue therapy for 2 years unless progression of disease or toxicity warranting discontinuation of therapy is observed.

Prednisone will be used orally at the dose of 30 mg/day during cycle 1, 15 mg/day during cycle 2, and 15 mg every other day during cycle 3, and then it will be discontinued.

All patients will be registered on the Patient Data Management System (PDMS) at MD Anderson Cancer Center after the informed consent is signed. Medication will be mailed to participants, per the RevAssist® Program.

5.1 Dose Modification Levels of Lenalidomide

Dose	Actions
Dose Level +3	25 mg on days 1-21 of every 28 day cycle
Dose Level +2	20 mg daily on days 1-21 of every 28 day cycle

Dose	Actions
Dose Level +1	15 mg daily on days 1-21 of every 28 day cycle
Level 0 (starting dose if platelet counts is $\geq 100 \times 10^9/L$)	10 mg on days 1-21 of every 28 day cycle
Dose Level -1 (starting dose if platelet counts is $< 100 \times 10^9/L$)	5 mg daily on days 1-21 of every 28 day cycle
Dose Level -2	5 mg every other day x 10 of every 28 day cycle

5.2 Instructions for Lenalidomide dose modifications or interruption during a cycle

CTCAE CATEGORY	ADVERSE EVENT	DOSAGE CHANGE
Allergy/Immunology	Allergic reaction/hypersensitivity (including drug fever) Grade 3	Omit lenalidomide for remainder of cycle. Restart at planned start of next cycle at the next lower dose level if adverse event reduces to \leq grade 1.
	Allergic reaction/hypersensitivity (including drug fever) Grade 4	Discontinue Lenalidomide
Blood/Bone Marrow	Neutrophils/granulocytes (ANC/AGC) Grade 4 or grade 3 associated with fever (38.5 degree centigrade or higher)	Omit Lenalidomide for remainder of cycle. Restart at planned start of next cycle at the next lower dose level if ANC $\geq 1000/\mu L$.
	Platelets \geq Grade 3 if $\geq 100 \times 10^9/L$ pretherapy or $< 50\%$ of pretherapy value if $< 100 \times 10^9/L$	Omit Lenalidomide for remainder of cycle. Restart at planned start of next cycle at the next lower dose level if platelet is $\geq 50 \times 10^9/L$ if $\geq 100 \times 10^9/L$ before starting therapy, or at least 50% of the pre-therapy value if $< 100 \times 10^9/L$ before starting therapy.
Cardiovascular	Sinus bradycardia/other cardiac arrhythmia Grade 2	Omit Lenalidomide for remainder of cycle. Restart at planned start

CTCAE CATEGORY	ADVERSE EVENT	DOSAGE CHANGE
		of next cycle at the next lower dose level if toxicity reduces to grade 1 or lower
	Sinus bradycardia/other cardiac arrhythmia Grade 3 or 4	Discontinue Lenalidomide
	Thrombosis/embolism Grade 3 or 4	Omit Lenalidomide for remainder of cycle and start systemic anticoagulation. Restart at planned start of next cycle at the same dose level at investigator's discretion and only if approved by the PI. (See section 5.5 for anticoagulation recommendations)
Dermatology/Skin	Rash/desquamation Grade 3	Omit Lenalidomide for remainder of cycle. Restart at planned start of next cycle at the next lower dose level if adverse event reduces to \leq grade 1.
	Rash/desquamation Grade 4	Discontinue Lenalidomide
	Rash: Erythema multiforme	Discontinue Lenalidomide
Endocrine	Hyperthyroidism/ Hypothyroidism	Omit Lenalidomide for remainder of cycle. Evaluate etiology, initiate appropriate therapy. Restart at planned start of next cycle at the next reduced dose level.
Other non-hematologic	Grade 3 or 4	Omit Lenalidomide for remainder of cycle. Restart at planned start of next cycle at the next lower dose level if adverse event reduces to \leq grade 2.

Dose escalation of lenalidomide may be indicated for patients with proliferative disease not controlled with combination of lenalidomide and prednisone after initial cycle of therapy. Dose escalation will only be allowed for patients who have not had any grade 2 or greater clinically relevant drug related non-hematologic toxicity with the prior cycle of therapy. Any other modifications in the dose of lenalidomide can be done if felt to be in the best interest of the patient, and approved by Principal Investigator.

5.3 Prednisone Dose Modifications

Dose modifications/discontinuation for prednisone therapy will be at the discretion of the clinician but must be documented clearly when it happens. Prednisone dose modification/discontinuation will not require withdrawal from the study; the patient may continue taking lenalidomide alone. Treatment of hyperglycemia with either oral hypoglycemic agents or insulin does not necessarily require discontinuation of prednisone if the hyperglycemia is controlled with these medications.

5.4 Initiation of a New Cycle of Therapy

A new course of treatment may begin on the scheduled Day 1 of a new cycle if:

- The ANC is $\geq 1,000/\mu\text{L}$;
- The platelet count is $\geq 50 \times 10^9/\text{L}$ if $\geq 100 \times 10^9/\text{L}$ before starting therapy, or at least 50% of the pre-therapy value if $< 100 \times 10^9/\text{L}$ before starting therapy;
- Any lenalidomide-related allergic reaction/hypersensitivity or sinus bradycardia/ other cardiac arrhythmia adverse event that may have occurred has resolved to \leq grade 1 severity;
- Any other lenalidomide-related adverse event that may have occurred has resolved to \leq grade 2 severity.

If these conditions are not met on Day 1 of a new cycle, the subject will be evaluated weekly and a new cycle of lenalidomide (with/without prednisone after cycle 3) will not be initiated until the toxicity has resolved as described above.

If lenalidomide dosing was omitted for the remainder of the previous cycle or if the new cycle is delayed due to toxicity newly encountered on the scheduled Day 1, then the new cycle will be started with a one-level dose reduction. If the toxicity has not resolved as described above within 4 weeks, the patient will discontinue treatment. In unusual circumstance this rule may be modified by Principal Investigator if felt to be in the best interest of the patient (for example, responding patient with neutropenia or low platelets, that resolve past 4 weeks may be restarted on therapy); this case must be fully documented.

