5.8 Evaluation During Study

Time parameters for mandatory evaluations during the study are: +/-5 days for blood tests, +/- two weeks for bone marrow exams, and +/-2 weeks for MD Anderson visits. Exception for these rules can be made in unusual circumstances (e.g. long holiday) if approved by Principal Investigator and documented.

- Follow up visits at MD Anderson are required initially monthly (+/- 1 week), with review of constitutional symptoms and physical exam. Following the completion of cycle 3, patients that are on a stable dose of lenalidomide and have no serious drug related side effects, and the physician feels it is in the patients best interest, may return to MDA every three months. Following the completion of cycle 24, patients that are on a stable dose of lenalidomide, have no serious drug related side effects, and the physician feels it is in the patients best interest, may return to MDA every 6 months (+/-2 weeks). Only one, 28 day supply of Lenalidomide may be provided to a patient per monthly cycle. In this case, a monthly phone assessment of toxicity, review of required blood tests (pregnancy test if applicable) and confirmation of the requirements for the initiation of a new cycle must be done.
- CBC with differential every other week x 8, then every 1 month or more frequently as clinically indicated. Following the completion of cycle 24, CBC every 1-3 months while participating on the study.
- Bone marrow aspiration and biopsy every 3 months (to include staining for fibrosis); cytogenetics every 3 months if abnormal prior to therapy; JAK2 mutation analysis every 3 months if mutation present prior to therapy. Following the completion of Cycle 24, bone marrow aspiration and biopsy every year, cytogenetics every year if abnormal prior to therapy; JAK2 every year if mutation present prior to therapy.
- Serum BUN, alkaline phosphatase, creatinine, bilirubin, ALT, sodium, potassium, chloride, carbon dioxide, glucose, lactate dehydrogenase every other week x 6, then every 1 month. Following the completion of cycle 24, complete every 3-6 months while participating on the study
- TSH every 3 months. Following the completion of Cycle 24, TSH every 6 months.
- CD34+ cell counts in blood every 3 months. Following the completion of Cycle 24 CD34+ every year.
- Serum or urine pregnancy test (sensitivity of at least 50 mIU/mL) every week x 4, then monthly for all FCBP with regular menstrual cycles, or every 2 weeks if irregular cycles.

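### After a grade 3 rash, section 5.2 holds lenalidomide until grade 1 or lower, but the rash condition in section 5.4 is already met at grade 2

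*Combined protocol and SAP*

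**What the plan says.** Section 5.2 has a Dermatology/Skin row, separate from the Allergy/Immunology row. For "Rash/desquamation Grade 3" the drug is omitted for the rest of the cycle, and the instruction continues: "Restart at planned start of next cycle at the next lower dose level if adverse event reduces to" grade 1 or lower.

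Section 5.4 lists what must hold before a new cycle starts. Besides neutrophil and platelet limits, it has two conditions on adverse events:

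- "Any lenalidomide-related allergic reaction/hypersensitivity or sinus bradycardia/ other cardiac arrhythmia adverse event that may have occurred has resolved to" grade 1 or lower.
- "Any other lenalidomide-related adverse event that may have occurred has resolved to" grade 2 or lower.

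Three further sentences in 5.4 depend on these conditions. On failure: "If these conditions are not met on Day 1 of a new cycle, the subject will be evaluated weekly". On dose, a one-level reduction applies "If lenalidomide dosing was omitted for the remainder of the previous cycle" or if a new toxicity delays the cycle. On stopping: "If the toxicity has not resolved as described above within 4 weeks, the patient will discontinue treatment", subject to an exception by the Principal Investigator in unusual circumstances.

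**The concern.** Both sections are operative dosing rules, and they give different answers for one patient: someone whose drug-related rash reached grade 3, led to omission of lenalidomide, and has fallen only to grade 2 by Day 1. Under 5.2 the drug is still held. Under 5.4 the rash is no bar to starting.

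A reader who follows 5.2 and waits then meets two further difficulties. The weekly evaluation in 5.4 starts only when a 5.4 condition fails, and a grade 2 rash does not fail one. It is also unclear whether the 4-week stopping rule measures resolution against the 5.2 limit or the 5.4 limit.

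What is at stake is consistent safety conduct for a few patients. The response endpoint and the two-stage design do not depend on it.

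**Working it through.** **Step 1: compare the limits.** The plan has no figure to reproduce here, so the check is a row-by-row comparison of every 5.2 restart limit with its counterpart in 5.4.

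| Event | 5.2 restart limit | 5.4 new-cycle limit | Agree? |
|---|---|---|---|
| Neutrophils | 1000/µL or more | 1000/µL or more | yes |
| Platelets | 50 x 10^9/L or more, or at least 50% of the pre-therapy value | same | yes |
| Allergic reaction | grade 1 or lower | grade 1 or lower | yes |
| Arrhythmia | grade 1 or lower | grade 1 or lower | yes |
| Other non-hematologic | grade 2 or lower | grade 2 or lower | yes |
| Rash/desquamation, grade 3 | grade 1 or lower | grade 2 or lower (general bullet) | **no** |

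Rash is the only stated limit that differs, which suggests it was left out of 5.4 by oversight. The sections are not full mirrors in other respects. The 5.4 event conditions cover only lenalidomide-related events, while the 5.2 rash row has no attribution limit. The 5.2 thrombosis row allows restart at the same dose level.

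**Step 2: trace the patient.** The rash is grade 3, so the drug is omitted (5.2). On Day 1 it is grade 2. The 5.2 limit is not met. The 5.4 rash condition is met. If the blood counts and other conditions also pass, 5.4 allows a start one dose level lower and no weekly evaluation begins.

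**Step 3: how many patients.**

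- Planned sample: 41 (section 9.0).
- Background rate: the single-agent lenalidomide study in myelofibrosis described in section 2.2 treated 41 patients and reported 1 rash of grade 3 or higher.
- Denominator: section 2.2 also says 20 patients were evaluable for response and toxicity. The reported 29% for any rash fits 12/41 = 29.3% but no count out of 20 (5/20 = 25%, 6/20 = 30%). So 41 is the better denominator, with 20 as a sensitivity case.

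Expected number = 41 x background rate:

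- Denominator 41: 41 x 1/41 = 1.0. The Clopper-Pearson 95% interval for 1/41 is 0.06% to 12.9%; times 41, this is 0.03 to 5.3.
- Denominator 20: 41 x 1/20 = 2.05, with interval 0.05 to 10.2.

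Only the share *s* of these at exactly grade 2 on Day 1 is affected. The documents do not give *s*. With denominator 41:

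| Assumed *s* | Affected patients | 95% interval |
|---|---|---|
| 0 | 0 | 0 |
| 0.5 | 0.5 | 0.01 to 2.6 |
| 1 | 1.0 | 0.03 to 5.3 |

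The background event is reported as grade 3 or higher. If it was grade 4, 5.2 would require discontinuation and the conflict would not arise.

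**The case against.** The best defence is that the two sections can both be obeyed. Section 5.4 is permissive and general, 5.2 is specific to the event, and waiting for grade 1 satisfies both. The person who held the drug did so under the very table row that states the grade 1 limit. This has force: 5.4 does not compel re-dosing, and a reader who applies both sections would wait. But no text sets precedence. Section 5.4 expressly deals with cycles that follow an omission, so someone checking Day 1 conditions has reason to treat it as complete. Waiting under 5.2 also does not start the weekly evaluation.

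On the 4-week rule, its paragraph opens with doses omitted in the previous cycle, so it may well reach the rash that caused the omission. That part is an ambiguity and not a demonstrated gap.

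Rash could also be classed as hypersensitivity and so reach the grade 1 bullet, but 5.2 lists the two in separate categories.

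A reader might infer that the phone checks in 5.8 make the error likely, because they confirm new-cycle requirements without a visit. The documents give this weak support. "Follow up visits at MD Anderson are required initially monthly", and the reduced schedule after cycle 3 is only for patients on a stable dose without serious drug-related side effects. A patient with a recent grade 3 rash and a pending dose reduction hardly fits, although a rash could arise after the switch to reduced visits.

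**Conclusion.** The inconsistency stands and is minor. As written, 5.4 lets a new cycle begin, as far as rash is concerned, for a patient whom 5.2 still holds.

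A reader might infer a full-dose rechallenge or unsupervised re-dosing. The documents do not support either. Both sections lower the dose by one level, section 8.0 leaves modifications to the treating physician or Principal Investigator, and section 5.10 removes patients whose severe toxicity does not respond to dose adjustment.

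The likely number affected is small, but about 1 of 41 is a point estimate and not a ceiling. The estimate assumes that the single-agent rate carries over. This trial doses on days 1-21, starts at 5 mg when platelets are low, and adds prednisone, which section 2.3 expects to improve tolerance, so the rate may differ. The mismatch between the sections does not depend on any of these rates.

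**What to change.** Add one bullet to 5.4 and leave the others unchanged: *Any rash/desquamation for which lenalidomide was omitted under section 5.2 in the previous cycle has resolved to grade 1 or lower.* State that the weekly evaluation and the 4-week rule apply to it.

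Tying the bullet to an omission under 5.2 matches that row, which has no attribution limit. Limiting it to the previous cycle avoids holding a patient for a new, milder rash long after an old one resolved. A rash that never exceeded grade 2 keeps its present limit, and the allergy and arrhythmia limits do not change.

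The cost is one bullet in a protocol amendment, with no extra patients and no extra scheduled tests. Weekly evaluation would be added only for the patients concerned.

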5.5 Concomitant Therapy

All medications (prescription and non-prescription), treatments and therapies taken from the first day of study through the end of study, must be recorded on the source documents.

The use of filgrastim (G-CSF) for subjects in this study is permitted when used to treat neutropenia secondary to therapy. Erythropoietin therapy is not allowed. Subjects should receive full supportive care, including transfusions of

blood products, antibiotics and antiemetics and prophylactic treatment for potential hypersensitivity reactions and tumor lysis syndrome when appropriate.

Prophylactic Anticoagulation:

Lenalidomide increases the risk of thrombotic events in patients who are at high risk or with a history of thrombosis, in particular when combined with other drugs known to cause thrombosis. When lenalidomide is combined with other agents such as steroids (e.g. dexamethasone, prednisone), anthracyclines (Doxil, adriamycin) and erythropoietin the risk of thrombosis is increased. Consideration should be given to the use of aspirin (81 or 325 mg) or some other form of prophylaxis as deemed appropriate. Low molecular weight heparin may be utilized in patients that are intolerant to aspirin. Coumadin should be used with caution and close monitoring of INR is required.

